**Figure 1. Study design**

## 6.2 Study Design Rationale

Need for a feasibility study: This study is based on the hypothesis that prolonged low dose IST will prevent GVHD exacerbation and need to resume of high doses of IST. Preliminary data in support of this hypothesis are derived from a retrospective study demonstrating that approximately half of patients with chronic GVHD who stop IST need to restart treatment after a median of 3-6 months. The only way to test this hypothesis is with a randomized trial but the sample size for such a study is prohibitive without evidence that patients can be enrolled and randomized, that they will follow their assigned treatment, and that the observations about IST resumption in the retrospective study appear accurate.

Justification for allowing heterogeneity in last agent, tapering schedules, and dose to continue in the intervention arm: As patients with chronic GVHD respond to a variety of immunosuppressive agents and doses, there is no unified treatment protocol for chronic GVHD. Similarly there are no uniform criteria when attempts to stop IST should be initiated. In our retrospective study the last immunosuppressive regimen to be discontinued was variable, including calcineurin inhibitors (43%), prednisone (28%), sirolimus (19%), or mycophenolate mofetil (10%). Thus, after discussion with the LTFU attendings, we elected to allow heterogeneity in plans for IST taper timing and speed. This study design mirrors routine clinical practice and allows us to capture data about the most common practices regarding IST discontinuation. At the time of enrollment, physicians must specify the dose/schedule at which they are comfortable randomizing a patient to possibly continue stable treatment for an additional 9 months. Ideally, this would be a dose that does not cause toxicity and also controls GVHD.

Enrollment time: We will enroll patients at the time when they are only taking one immunosuppressive agent, chronic GVHD is under control and the plan is to start tapering IST, or when patients are already tapering IST. Patients may be enrolled on the study before or at the time they are taking the IST dose that the attending physician recommends they continue should they be randomized to the continuation IST arm. Enrolling patients before or at the time they reach the IST dose that may be continued should they be randomized to the continuation IST arm (Figure 1) allows us to present the protocol to patients when they are seen in the clinic, which will increase the chance of enrolling patients on the study (Patients with well controlled GVHD are seen in clinic infrequently and thus may be seen before or at the time they have already reached the lower IST dose to be continued).

## 6.3 Subject Registration and Informed Consent

Eligible subjects will be identified by the SCCA LTFU or SCH providers and the study staff. A complete, signed, study informed consent is required for registration.

Before enrollment, the study investigator or sub-investigators will discuss the study and consent form thoroughly with the potential participant. The study will be presented as objectively as possible and the potential risks and hazards of the study explained to the

subject. Consent will be obtained using forms approved by the Institutional Review Board of the Fred Hutchinson Cancer Research Center (FHCRC).

The study and consent form will be discussed with potential participants at their LTFU at the SCCA or SCH visits. However, if the patient requests to think about the study prior to making final decision, the study PI or sub-PI will call the patient about a week after his/her appointment, will review the study and consent form again, answer any questions the patient might have, and if the patient is interested he/she will sign consent over the phone. The rational for the telephone follow-up and not in person follow-up is that many of the patients are not local, and the phone follow-up will decrease burden on the patient. If patient would like to have in person follow-up this option would be available.

If subject signs the informed consent at home (after discussing the study procedure and its potential risk with the study investigator or sub-investigator), he/she will mail the signed informed consent form (ICF) to the FHCRC and the document will be signed by the person who obtained the consent over the phone. The investigator/sub-investigator will document the consent discussion in the medical record. A copy of the ICF will be provided to the subject. Signed ICFs will remain in each subject's chart.

#### 6.4 Data Collection

Provider and patient assessments will be collected in the form of study surveys at enrollment, and if possible at randomization, and every three months for 12 months and at times of IST resumption or increased dose, if still during the period of active study participation. If patients cannot be seen at the SCCA or SCH clinic at these time points, an effort will be made to collect the pertinent information from the patients' local providers. The study team will contact participants monthly via phone or email to check on each patient's status. Additional information (e.g. laboratory test results) would be obtained from the patients' records.

For further evaluation of patients' health status, adult participants will be asked to complete a survey based on the PROMIS-29 and Lee symptoms scale (Appendix A). Patients will be asked to complete the survey at enrollment, randomization, every 3 months after randomization, at the end of the active study participation (12 months after randomization) and if IST resumed/dose increased (if still during the active study participation period). If a patient is not seen in clinic, questionnaires will be mailed to the patient.

Following the 12 months active participation period, participants will be followed by chart review annually to determine disease status, GVHD status, IST status, and survival.

#### 6.5 Study Procedures

Eligible patients will be identified at Seattle Cancer Care Alliance or Seattle Children's Hospital by clinicians. Signed informed consent will be obtained by clinicians. All

females of childbearing potential will have a pregnancy test at enrollment. Pregnant women will be excluded from the study.

After consent, the clinician will complete the provider survey, the patient will complete the patient self-assessment survey, and an effort will be made to have a research blood sample drawn.

If patients are enrolled on the study prior to reaching the IST dose the attending physician recommends they continue should they be randomized to the continuation IST arm, then randomization will take place before the patient gets to the IST dose that would be continued if they are randomized to the IST continuation arm (investigational arm). If patients are enrolled on the study while they are already taking the IST dose that the attending physician recommends they continue should they be randomized to the continuation IST arm, randomization will take place at time of enrollment (Figure 1).

The clinician and the patient will be informed about the randomization, and further IST management would be according to the study arm the patient was randomized to, as described above.

There is no financial compensation to patients for participating in this study.

Participants will be contacted by the study coordinator via phone or email (according to their preference) monthly, if they are not seen at the LTFU clinic. The study coordinator will review health status, confirm future clinic schedules and check whether IST was restarted for GVHD. Following the 12 months active participation period, participants will be followed by chart review annually to determine disease status, GVHD status, IST status, and survival.

Research blood samples will be collected from patients at time of enrollment, and potentially several time points after enrollment as discussed above in section 6.1.

Data will be entered electronically into a password-protected database using only the participant study ID. All data will be maintained in secured areas (locked file cabinets and password-protected electronic databases).

If a patient relapses with their primary disease and requires systemic anti-cancer treatment, data collection from the patient and clinician will cease and no additional research samples will be taken. The patient will continue to be followed via chart review.

The intent is to randomize patients within three months of enrollment. If a patient has not been randomized within three months of enrollment, data collection from the patient and clinician will cease and no additional research samples will be taken. The patient will continue to be followed via chart review.

If a participant or the partner of a research participant becomes pregnant during the study, the principal investigator will follow the pregnant female for pregnancy outcome.

## 6.6 Adverse Reactions and their Management

Prolonged IST on the continuation IST arm may result in increased risk of infection, treatment related organ toxicity, and increased risk for relapse. Earlier discontinuation of IST on the discontinuation arm may result in increased risk for GVHD exacerbation, required initiation of high dose immunosuppression, which again may result in increased risk of infection, treatment related organ toxicity, and increased risk for relapse. Treatment of any complication will be at the discretion of the patient's provider.

Blood collection for research purposes will usually be done at the same time as clinical sampling.

If an adverse event occurs as a result of study participation, the PI will ensure appropriate follow-up is carried out until the effects of the adverse event are resolved. If the study staff becomes aware of any unanticipated severe adverse reactions due to study participation, the circumstances will be reported to the IRB. To note, clinical events and/or laboratory findings related to IST will not be reported as adverse events, since both discontinuation or prolonged continuation of IST are used in practice.

## 6.7 Data and Specimen Storage

Blood samples will be collected for future laboratory studies. Participants will donate whole blood at enrollment and additional time points as detailed in section 6.1. Samples will be processed according to standard procedures and labeled with a sample identification number. Samples will be stored in a repository and may be used to study chronic GVHD and/or other transplant complications.

All study data will be stored in the master database using only the participant's unique identifier. The link to the participant's identity will be maintained separately from the study data.

# 7. Statistical Considerations

## 7.1. Statistical Analysis Plan

### 7.1.1. Primary Endpoint

The primary objective of this study is to assess feasibility of enrolling and randomizing patients with chronic GVHD to discontinuation (discontinuation IST arm; standard of care) versus prolonged continuation of IST (continuation IST arm; investigational arm).

Feasibility will be assessed by accrual rate of 20 patients per year. Early stopping of the accrual to the study is low accrual rate defined as less than 12 patients enrolled in the first year.

### 7.1.2. Secondary Endpoints

The secondary objective of this study includes three parts: 1) treatment compliance including rate of patient reaching randomization and rate of patients following study specific IST management based on study arm; 2) assess feasibility (enrollment and data collection) for patients who are not local; and 3) assess whether continuation IST decreases the need for pulses of high does IST and efficacy and safety evaluation of continuation IST arm

Secondary endpoint analyses will be descriptive. The analyses will be conducted by overall population, patients who are not local, and by arm, as applicable.

The summary statistics for continuous variables will include sample size, mean, standard deviation (SD), median, minimum and maximum for both baseline and post-baseline measurements (if applicable). The summary statistics for categorical variables will include sample size, frequency and percentages. The difference between two arms will be examined if applicable. Fisher's exact test will be proposed to test the difference between two arms for categorical variables.

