## 1. Background and Rationale

Patients who received allogeneic hematopoietic cell transplantation (HCT) typically require administration of immunosuppressive treatment (IST) for at least 6 months in order to prevent or treat graft-versus-host disease (GVHD). GVHD is the most serious and common complication of allogeneic HCT. Significant acute GVHD occurs in 20-50% of patients,(1-3) and chronic GVHD occurs in 30-60% of patients who survive more than 100 days after transplantation.(3, 4) Duration of IST is typically prolonged once patients develop GVHD. Particularly, duration of IST in patients who have chronic GVHD is reported to exceed 2-3 years.(5, 6) While IST is important to reduce mortality and morbidity associated with GVHD, it may increase risks of infection, recurrent malignancy and secondary malignancy.(7)

“Immunologic tolerance” may be defined as the absence of immune-mediated injury when immunosuppressive medications are no longer given. Unlike solid organ transplantation,(8) many patients after allogeneic HCT can achieve sufficient “functional” tolerance even after development of GVHD, and can eventually stop all IST permanently without developing active manifestations of GVHD. However, many patients, especially those with chronic GVHD, develop GVHD exacerbation and require resumption of IST. Currently, there are no clinical or biological predictors for successful IST discontinuation, and management of chronic GVHD patients consists of repeated attempts to taper and stop IST.

A recent retrospective evaluation of 250 adult patients who received systemic treatment for chronic GVHD at the Fred Hutchinson Cancer Research Center (FHCRC)/Seattle Cancer Care Alliance (SCCA) demonstrated that although 51% patients were able to stop IST at least one time, 46% of these patients required resumption of IST after a median of 3.4 months off therapy (IQR 2.1-8.0), due to GVHD exacerbation (9). Among patients stopping IST a second time, 30% restarted at a median of 6 months.

Resumption of IST for chronic GVHD exacerbation may increase the morbidity and mortality of patients, since common practice is to reinstitute high doses of IST initially, followed by a taper again to the lowest dose. Additionally, GVHD may fail to be controlled after resumption of IST, or irreversible organ damage may occur each time GVHD symptoms flare.

A potential alternative approach to the current practice of repeated attempts to taper and stop IST is continuation of IST.

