## 7.2. Sample Size and Power

This feasibility study is to assess the ability to enroll and randomize patients with chronic GVHD to discontinuation versus continuation of IST. Sample size of 40 patients is based on the anticipated availability of eligible patients. Although the study is not powered based on a specific null hypothesis, if 20 patients are enrolled in each arm, we will have 83% power to see statistically significant difference between two arms (at the two-sided level of 0.1) if the true 12 months rate of IST resumption in discontinuation IST arm is 75% and true 12 months rate of increase IST dose in investigation arm is 30%.

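### For the 12-month IST resumption/increase comparison, Boschloo's exact test would keep the 0.10 level and give about 7 points more power than Fisher's at exactly 20 per arm (an optional gain, not an error)

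*Combined protocol and SAP*

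**What the plan says.** Section 7.1.2 says of the secondary endpoints: "Secondary endpoint analyses will be descriptive". It then adds a test: "Fisher's exact test will be proposed to test the difference between two arms for categorical variables". Section 7.1.3 repeats that sentence. Neither section sets a significance level, and neither asks for a confidence interval for the difference between arms.

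A level appears only in section 7.2, and only for one comparison. That section says the study is not powered on a specific null hypothesis and that the 40 patients reflect expected availability. It continues: "if 20 patients are enrolled in each arm, we will have 83% power", with the test taken "at the two-sided level of 0.1". The event rates assumed for this are 75% with discontinuation and 30% with continuation.

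For context, section 1 reports from the retrospective cohort that, among patients who stopped IST, "46% of these patients required resumption of IST after a median of 3.4 months off therapy". Section 9 rounds this to about 50%.

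**The concern.** Fisher's test conditions on the total number of events. With 20 per arm this leaves few attainable p-values, and the test rejects less often under the null hypothesis than its nominal level allows. The plan declares a two-sided 0.10 level for this comparison, but at 20 per arm the test uses only about half of it.

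An uncorrected chi-square test would be a doubtful remedy, because its true level can exceed the nominal one. Boschloo's test does not have that drawback. It takes Fisher's p-value as its ordering statistic and calibrates it against the worst-case common event rate, so its level is guaranteed.

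This is the only comparison for which the plan states a power, and section 7.2 ties the sample to patient availability. The choice of test is therefore one of the few ways to make the comparison more sensitive. An observed 13/20 vs 7/20, a 30-point difference, has p = 0.113 with Fisher's test and p = 0.081 with Boschloo's.

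**Working it through.** **Inputs.** From section 7.2: n = 20 per arm, rates 0.75 and 0.30, two-sided level 0.10, stated power 83%. From section 1: 46% as a lower discontinuation-arm rate. That figure is not a 12-month rate, so it serves only for sensitivity. The documents give no continuation-arm rate other than 30%; the 20% used below is an assumption.

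**Formulas.** Let A and B be independent binomial counts in the two arms, and F(a,b) the two-sided Fisher p-value.
- Power = sum over all 21 × 21 pairs (a,b) of Bin(a; 20, 0.75) × Bin(b; 20, 0.30) × 1{table rejected}.
- Size at a common rate π = the same sum with both rates equal to π; the maximum is taken over a fine grid of π.
- Fisher rejects when F(a,b) ≤ 0.10.
- Boschloo p-value = maximum over π of P{F(A,B) ≤ F(a,b)}; it rejects when this is ≤ 0.10.

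**Step 1: the plan's own figure.** Fisher's test gives 82.3%, close to the stated 83%. A continuity-corrected normal formula gives 84.0%. The uncorrected pooled normal formula gives 91.1% and does not match. The stated power agrees with the stated test.

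**Step 2: level used at 20/20.**
- Fisher: maximum size 5.3%, at π of about 0.32. At the pooled design rate (0.75 + 0.30)/2 = 0.525 it is 4.3%. As shares of the level: 5.3/10 = 53% and 4.3/10 = 43%.
- Boschloo: maximum size 8.6%, and 8.1% at 0.525. Both lie below 10%.

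**Step 3: rejection regions at 20/20.** Boschloo rejects every table that Fisher rejects. It adds eleven tables and their mirror images, among them 15/20 vs 9/20 (Fisher p = 0.105, Boschloo p = 0.061) and 13/20 vs 7/20 (0.113 and 0.081).

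**Step 4: power at 75% vs 30%.** 89.1 − 82.3 = 6.8 points.

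**Step 5: other arm sizes.** Same calculation, 75% vs 30%, in per cent. Gains are taken before rounding.

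| Arms | Fisher maximum size | Fisher power | Boschloo power | Gain (points) |
|---|---|---|---|---|
| 20/20 | 5.3 | 82.3 | 89.1 | 6.8 |
| 21/19 | 7.0 | 84.7 | 89.8 | 5.0 |
| 22/18 | 6.8 | 84.0 | 90.2 | 6.3 |
| 19/19 | 5.8 | 82.3 | 87.3 | 5.0 |
| 19/18 | 8.0 | 85.0 | 89.0 | 4.0 |
| 18/18 | 6.5 | 83.5 | 84.9 | 1.4 |
| 19/17 | 7.6 | 84.5 | 85.5 | 1.0 |
| 18/16 | 7.2 | 81.4 | 83.5 | 2.1 |
| 17/17 | 5.8 | 79.9 | 82.6 | 2.7 |
| 16/16 | 5.0 | 75.5 | 80.5 | 4.9 |
| 15/15 | 4.3 | 70.4 | 82.3 | 11.9 |

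Boschloo's maximum size lay between 8.6% and 9.9% at these sizes, and its rejection region contained Fisher's each time.

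**Step 6: lower rates, 46% vs an assumed 20%.** At 20/20, power goes from 43.3% to 51.4%, about 8 points. In smaller equal arms the gain is 10.5 (19/19), 10.8 (18/18), 11.5 (17/17), 11.7 (16/16) and 13.6 (15/15). In the unequal arms of the table it is about 3 to 6 points.

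**The case against.** The strongest reply is that nothing here is wrong. Fisher's test is valid and conventional for small two-by-two tables, and the test, level and power in the plan agree with one another. A reader might infer that the 83% is overstated or that the test was misapplied; Step 1 shows neither. This part of the reply stands in full.

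The second reply is that the headline figure depends on exact balance. It does. Section 3.1 counts signed consents, section 6.5 ends data collection for patients not randomized within three months, and no blocking is described, so 20 analysable patients per arm are not assured. Fisher uses 70% to 80% of the level at 21/19 and 19/18, and the gain at the design rates falls to 1.0 point at 19/17. A general statement that Fisher's test wastes half its level, or that about 7 points are always to be had, is therefore not supported. What survives is that Boschloo was never worse at any size checked.

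The third reply is that no decision turns on this test. The primary endpoint is enrollment, the only stopping rule is accrual, and estimated rates matter more than a p-value for planning the larger trial. That limits the importance of the point. It does not remove it, because the plan still names a test and gives its level and power.

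Finally, the 0.10 level is stated for one comparison only. The size figures cannot be carried over to the other categorical variables, for which no level is set.

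**Conclusion.** The point holds as an optional efficiency improvement to one secondary, descriptive comparison. At exactly 20 per arm, 75% vs 30% and two-sided 0.10, replacing Fisher's test with Boschloo's raises power from 82.3% to 89.1% and keeps the true level at or below 8.6%. At the design rates the gain is 1.0 to 6.3 points at the other sizes from 16 to 22 per arm in the table, and 11.9 at 15/15.

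The calculation assumes independent binary outcomes known for every patient analysed and, in the lower-rate scenario, a continuation-arm rate of 20% that the documents do not give.

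It would go too far to conclude that the trial is underpowered because of its test, or that its feasibility conclusion is affected. The study is not sized on this comparison, and its primary endpoint does not use the test.

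**What to change.** Before outcome data are examined:

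1. In sections 7.1.2 and 7.1.3, name Boschloo's exact unconditional test, two-sided at 0.10, for the binary 12-month IST resumption/dose increase comparison. Keep Fisher's exact test for variables with more than two categories.
2. Report the risk difference for this comparison with a 90% confidence interval, and name the interval method in advance. For a descriptive study that is to inform a larger one, the interval is more useful than the p-value.
3. In section 7.2, name the test behind the power statement and restate it as about 89% at exactly 20 per arm, with a note that it varies with arm size. If Fisher's test is kept, the present 83% can stand.

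The cost is a few sentences of SAP text and a test available in standard software. No patients or procedures are added, and type I error control at 0.10 is retained.

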### 2.2 Secondary Objectives

- Assess feasibility of enrolling and randomizing patients who are not local, and evaluate the quality of data received for those patients.
- Assess whether prolonged IST decreases the need for pulses of high dose IST.
- Evaluate the effect of prolonged IST on chronic GVHD manifestations and severity, risk of relapse, infection and organ toxicity.

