### 7.1.3. Methods

Descriptive summary table will be provided for overall study population, and by each arm, respectively. The summary statistics for continuous variables will include sample size, mean, standard deviation (SD), median, minimum and maximum for both baseline and post-baseline measurements (if applicable). The summary statistics for categorical variables will include sample size, frequency and percentages. The difference between the two arms will be examined if applicable. Fisher's exact test will be proposed to test the difference between two arms for categorical variables.

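### The harm endpoints get a Fisher p-value but no risk difference or interval, and at 20 per arm that p-value says little about harm in either direction

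*Combined protocol and SAP*

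**What the plan says.** Section 2.2 makes harm a secondary objective: "Evaluate the effect of prolonged IST on chronic GVHD manifestations and severity, risk of relapse, infection and organ toxicity". Section 3.2 lists the matching endpoints: new or worsening chronic GVHD, recurrent malignancy by 12 months, grade 3 or higher infection, and grade 3 or higher organ toxicity. Section 7.1.2 carries this forward as "efficacy and safety evaluation of continuation IST arm".

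On direction, section 6.6 warns: "Prolonged IST on the continuation IST arm may result in increased risk of infection, treatment related organ toxicity, and increased risk for relapse". Section 8 repeats the warning. Both sections add that stopping may lead to a flare and high-dose treatment, and through that to the same three harms.

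On analysis, section 7.1.2 labels the secondary endpoint analyses descriptive. In section 7.1.3, "The summary statistics for categorical variables will include sample size, frequency and percentages". Both sections say that the difference between the arms will be looked at where applicable, without naming an effect measure, and both end with the same sentence: "Fisher's exact test will be proposed to test the difference between two arms for categorical variables". Neither names a risk difference, a confidence interval or a bound.

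Section 7.2 has the only power figure: "if 20 patients are enrolled in each arm, we will have 83% power to see statistically significant difference between two arms". It is calculated for a two-sided test at 0.10 and for 12-month rates of 75% (IST resumption on discontinuation) and 30% (dose increase on continuation). It concerns IST use and not a harm.

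**The concern.** At this sample size a descriptive harm analysis needs an estimate of the difference and its uncertainty. The plan specifies the percentages and a significance test, but nothing that shows how large a difference the data leave open. The test was shown to have good power only for a 45-point difference (75% minus 30%). Harms may well differ by much less, and there a non-significant result is likely whether or not the arms truly differ.

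Two features raise the stakes. Section 1 says the results are needed to design a larger study and seek funding, so the harm tables are likely to be read with that trial in mind. Sections 6.6, 10.1 and 10.5 also keep clinical events related to IST out of adverse event reporting, so the endpoint tables by arm carry more of the harm information than they otherwise would.

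**Working it through.** **Inputs.** From section 7.2: 20 per arm, and a two-sided 0.10 level stated only for the IST endpoint. From 7.1.2 and 7.1.3: Fisher's exact test. Assumed, because the documents give none: control (discontinuation) harm rates of 5% to 30%, a doubling on continuation, and the 0.10 level for harms (0.05 is also shown).

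**Formula.** With i events of 20 on discontinuation and j of 20 on continuation, power = Σᵢ Σⱼ Bin(i; 20, p_D) × Bin(j; 20, p_C) × 1[Fisher p(i, j) ≤ α], summed over all 21 × 21 tables. Miss rate = 1 − power.

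**Step 1: the plan's own figure.** p_D = 0.75, p_C = 0.30 and α = 0.10 give power 0.823, against the stated 83%. The method agrees with the plan.

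**Step 2: a doubled harm.**

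| Discontinuation vs continuation | Missed, α = 0.10 | Missed, α = 0.05 |
|---|---|---|
| 5% vs 10% | 98.0% | 98.3% |
| 10% vs 20% | 89.0% | 92.8% |
| 15% vs 30% | 80.1% | 87.6% |
| 20% vs 40% | 70.9% | 80.8% |
| 25% vs 50% | 62.5% | 73.1% |
| 30% vs 60% | 53.7% | 65.3% |

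The two-sided test with equal arms is symmetric, so the same figures hold if the doubled rate is on discontinuation. At higher rates the problem fades: 40% vs 80% is missed 24.7% of the time at 0.10. Fewer randomized patients make it worse: for control rates of 20% down to 10% at 0.10, the miss rate is 74% to 91% with 18 per arm and 79% to 93% with 16.

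**Step 3: what the test needs to see.** With 2/20 events on discontinuation, 6/20 on continuation gives p = 0.24 and 7/20 gives p = 0.13. Only at 8/20 does p fall to 0.10 or below (0.065).

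**Step 4: what an interval would add.** The Newcombe 90% interval combines the Wilson limits of each arm, (p + z²/2n ± z√(p(1−p)/n + z²/4n²)) / (1 + z²/n), with z = 1.645 and n = 20. Wilson limits: 2/20 gives 0.034 to 0.262; 6/20 gives 0.164 to 0.484; 7/20 gives 0.202 to 0.533.

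- 2/20 vs 6/20: difference 0.30 − 0.10 = 0.20. Lower limit 0.20 − √((0.30 − 0.164)² + (0.262 − 0.10)²) = −0.01. Upper limit 0.20 + √((0.484 − 0.30)² + (0.10 − 0.034)²) = 0.395. The interval runs from about −1 to +40 points, beside p = 0.24.
- 2/20 vs 2/20: 0 ± √((0.262 − 0.10)² + (0.10 − 0.034)²) = ±0.175. Identical counts still leave an excess of about 17 points open on either arm, beside p = 1.0.
- 2/20 vs 7/20: difference 0.25. Lower limit 0.25 − √((0.35 − 0.202)² + (0.262 − 0.10)²) = 0.03. Upper limit 0.25 + √((0.533 − 0.35)² + (0.10 − 0.034)²) = 0.44. Here the interval excludes zero although p = 0.13, because Fisher's test is conservative at this size. The two summaries can disagree, so the plan should say which one leads.

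**The case against.** The strongest reply is that this is a feasibility study and the plan says so. Section 7.1.2 calls these analyses descriptive. Section 7.2 says the size reflects how many eligible patients are expected, and that the trial was not sized to test a particular hypothesis. Section 1 says that showing significant differences takes a large trial. Percentages by arm will be printed, so 10% vs 30% would be visible whatever the p-value, and anyone with the counts can work out the interval. Low power for uncommon harms comes with 40 patients and is not an analysis mistake.

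All of that stands, and it rules out several stronger readings. A reader might infer that the safety evaluation rests on the test, or that a null result would be presented as no harm. The documents do not support this: the percentages come first, and no section treats non-significance as safety. A reader might take 71% to 89% as a property of the plan. It is not: it depends on assumed control rates and on a level that section 7.2 states only for IST resumption or dose increase. A reader might frame the risk as excess harm from continuation alone, but sections 6.6 and 8 expect the same harms after a flare on discontinuation. A reader might ask for a safety margin, but none is needed, because the plan makes no claim to exclude harm.

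The reply does not defend the choice of tool. A descriptive analysis of a small trial is better served by an estimate with an interval than by a test. The general remarks about sample size do not tell a reader how to take a null harm result, and the planned tables would not show the uncertainty.

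**Conclusion.** The point holds as a low-cost improvement to reporting and not as an error in the plan. For the harm endpoints, Fisher's test is the only between-arm inferential tool named, with no effect measure or interval beside it. With 20 per arm and an assumed two-sided 0.10 level, it would miss a true doubling about 71% to 89% of the time for control rates of 20% down to 10%, and about 54% to 98% across 30% down to 5%. The rates, the doubling and the level for harms are assumptions. The conclusion survives a change to 0.05, which raises every miss rate in the table, but weakens if harms are common. The primary feasibility endpoint, the sample size and the data collection are unaffected.

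**What to change.** In sections 7.1.2 and 7.1.3, for recurrent malignancy, grade 3 or higher infection, grade 3 or higher organ toxicity, and new or worsening chronic GVHD:

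- Make the risk difference (continuation minus discontinuation) with a two-sided 90% interval, for example Newcombe, the main between-arm summary. Each limit then serves as an approximate one-sided 95% bound on the excess harm in that direction.
- Make the Fisher p-value supportive or drop it. If it is kept, say that the interval leads where the two disagree.
- Add a sentence such as: *A non-significant difference between arms in a harm endpoint will not be read as evidence of no harm; the interval limits will be reported as the excess risk that the data do not exclude.*

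The cost is a few sentences in section 7 and one more column in the harm tables, with no new patients or data. The downside is that the wide intervals make the safety summary less reassuring.
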